### 4.1 Summary of study design

This study will be conducted as a phase III randomised, open-label, non-inferiority multicentre international trial.

A total of 250 people with recently acquired hepatitis C will be enrolled and randomised.

The number of participants with HCV/HIV coinfection enrolled to the study will be capped at 70% (or less than 175 participants) of the total study population. In addition, the number of participants with HCV reinfection enrolled to the study will be capped at 20% (or less than 50 participants) of the total study population.

The study consists of a screening phase (-12 to -4 weeks), treatment commencement from baseline, randomisation between week 5 and 6, treatment for another 6 weeks for those randomised to standard therapy (12 weeks of treatment) or end of treatment for those randomised to shortened treatment (6 weeks of treatment). All participants will then enter the follow-up phase (96 weeks) to evaluate treatment response and reinfection (Figure 1). Randomisation will be using blocks and will be stratified by study site and HIV status.

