#### 4.2 Visit Schedule

All participants will complete screening, on-treatment and post-treatment assessments as outlined in the Schedule of Assessments in Section 6.0.

Screening assessments must be completed within 12 weeks prior to baseline. There must be a minimum of 4 weeks between screening and baseline.

Following screening, eligible participants will commence treatment. Between week 5 and week 6 of treatment, the participants will be randomised to either the shortened or standard treatment duration. On-treatment visits will be conducted at weeks 1, 2, 4 and 6 (end of treatment for participants on shortened treatment duration), weeks 8 and 10 (for participants on standard treatment duration only). Participants on standard treatment duration will attend end of treatment at week 12. For participants randomised to shortened treatment, follow-up visits will be conducted at week 10 (SVR4), week 18 (SVR12), week 30 (SVR24), week 42 (FU1), week 54 (FU2), week 66 (FU3), week 78 (FU4), week 90 (FU5) and week 102 (Termination). For participants randomised to standard treatment, follow-up visits will be conducted at week 16 (SVR4), week 24 (SVR12), week 36 (SVR24), week 48 (FU1), week 60 (FU2), week 72 (FU3), week 84 (FU4), week 96 (FU5) and week 108 (Termination).

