The modified Intention to Treat (mITT) population includes participants in the FAS excluding those with non-virological reasons for treatment failure (i.e., death, loss to follow up) and reinfection. Participants with confirmed reinfection after achieving an ETR, but prior to the primary efficacy endpoint (SVR12), will be excluded from the mITT.

Per-protocol Analysis Set

The PP population is defined as all participants who received >90% of scheduled treatment for >90% of the scheduled treatment period with follow-up virologic data to SVR12.

Safety Population

The Safety population includes all participants who randomised and will be analysed and presented according to the actual on-treatment monitoring arm received during the study.

The ITT population will be used for primary efficacy analyses, and the safety population will be used for all safety analyses.

Data Handling Conventions

Missing Data

For the analyses of categorical HCV RNA data, missing post-treatment HCV RNA data will have the missing data imputed. Missing on-treatment HCV RNA will have the missing data imputed up to the time of the last dose.

If a data point is missing and is preceded and followed in time by values that are "<LLOQ, TND," then the missing data point will be set to "<LLOQ, TND."

If a data point is missing, and preceded and followed by values that are "<LLOQ, target detected," or preceded by "<LLOQ, target detected" and followed by "<LLOQ, TND," or preceded by "<LLOQ, TND" and followed by "<LLOQ, target detected," then the missing value will be set to "<LLOQ, target detected."

If a data point is missing, and preceded and followed by values that are ">LLOQ, target detected," or preceded by ">LLOQ, detected" and followed by "<LLOQ, target detected" or "<LLOQ, TND", then the missing value will be set to ">LLOQ, target detected."

The following scenarios describe a framework for analysis of the primary endpoint based on various anticipated events for the ITT and mITT population:

- i. In the event of the participant dying or becoming lost to follow-up prior to SVR 12, the participant will be considered to have failed treatment (loss to follow up = failure)
- ii. If the SVR 12 time-point measure is missing, then the next available measure (i.e., SVR 24 or later) will be used. If no future time points are available, the participant will be considered a treatment failure.

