	To evaluate patient interest and attitudes towards long acting parenteral hepatitis C therapy (Long-Acting Hepatitis C Therapy Questionnaire)	Not included in primary analysis	

Primary efficacy endpoint

The proportion of participants with HCV RNA below the level of quantitation (target not detected [TND] or target detected, not quantifiable [TDnq]) at 12 weeks post end of treatment (SVR12)

The primary analysis will compare randomised treatment groups on an ITT basis including all available data. The primary endpoint, SVR12, will be calculated for each patient based on all available data. Treatment arms will be regarded as non-inferior if the difference in proportion between regimens has a lower limit greater than -12%. Secondary analyses will compare randomised treatment groups based on available data (per protocol).

Secondary efficacy endpoints

- Virological endpoints
 - The proportion of treated participants with:
 - ETR (defined as undetectable plasma HCV RNA at the end of treatment)
 - SVR4 (defined as undetectable plasma HCV RNA at post-treatment week 4)

For virological endpoints, the point estimates and 95% exact confidence intervals will be reported by study arm, by HCV genotype and by HIV serostatus.

Virological endpoints (Table 13 and 14)

The presence of HCV RNA will be assessed at all scheduled clinic study visits using Aptima HCV Quant Dx assay, version 2.15.5 (lower limit of quantitation [LLOQ] 10IU/mL; Hologic, Inc., Marlborough, MA, USA), with centralised testing performed at St Vincent's Centre for Applied Medical Research (Sydney, NSW, Australia).

Proportions and 95% confidence intervals will be reported for both the primary and secondary virological endpoints. Virological endpoints will be assessed in the ITT, mITT and PP populations, with results stratified by HCV genotype/subtype and HIV serostatus.

Factors associated with treatment outcome in the ITT population will be evaluated by univariate analysis. Variables assessed will include but are not limited to: demographic factors (age, gender); virological factors (baseline HCV RNA, genotype 1 subtype, duration of HCV infection); risk behaviors (injecting drug use, sexual behavior, mode of HCV acquisition); HIV co-infection; treatment factors (adherence).

Primary safety endpoints

The primary safety endpoints are:

- Proportion of participants with common adverse events (reported by greater than 5% of the study population);

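### Loss before SVR12 counts as failure and the standard arm has about 6 more weeks after randomisation in which to be lost, so the primary ITT decision may lean toward non-inferiority; no second analysis has to agree with it

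*SAP*

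**What the plan says.** Protocol section 4.1 puts "randomisation between week 5 and 6", during treatment that both arms share. Under Protocol section 4.2, short-arm "follow-up visits will be conducted at week 10 (SVR4), week 18 (SVR12), week 30 (SVR24"), and standard-arm "follow-up visits will be conducted at week 16 (SVR4), week 24 (SVR12), week 36 (SVR24").

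The SAP's Missing Data section sets two rules for the primary endpoint. Under scenario i, a participant "becoming lost to follow-up prior to SVR 12, the participant will be considered to have failed treatment". Scenario ii softens this: "If the SVR 12 time-point measure is missing, then the next available measure (i.e., SVR 24 or later) will be used". Only participants with no later value end as failures.

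The decision rule under Primary efficacy endpoint is applied to the ITT comparison: "Treatment arms will be regarded as non-inferior if the difference in proportion between regimens has a lower limit greater than -12" per cent. Table 12 of the SAP also lists non-inferiority in the modified ITT (mITT) and per-protocol (PP) sets as secondary endpoints. The mITT set excludes deaths, losses and reinfections. The PP set requires more than 90% of treatment and virological data to SVR12.

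**The concern.** Follow-up to the endpoint is counted from the end of treatment, but the arms are compared from randomisation. At the same weekly loss rate, the 12-week arm collects more losses before SVR12 simply because its endpoint comes 6 weeks later. Each unrecovered loss is scored as a failure whatever the drug did. Extra non-virological failures in the control arm move the 6-week minus 12-week difference upward, which is the anti-conservative direction for a non-inferiority claim. The primary verdict depends on that one lower limit.

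**Working it through.** **The plan's own figure.** 113 per arm for 80% power, 90% SVR and a 12-point margin. The unpooled formula gives 2 × 0.9 × 0.1 × (1.960 + 0.842)² / 0.12² = 98.1, so 99. A continuity correction gives 114.2 and Farrington-Manning 110.2. Exact power at 113 per arm is 80.0% with a continuity-corrected Wald interval. So 113 is reproducible to within about 3%. Neither document links it, or the step from 2 × 113 = 226 to 250, to loss to follow-up, so no loss rate can be read from the sample size.

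**Time at risk** (randomisation at the midpoint, week 5.5):
- standard arm: 24 - 5.5 = 18.5 weeks
- short arm: 18 - 5.5 = 12.5 weeks
- ratio: 18.5 / 12.5 = 1.48 (19/13 = 1.46 if randomised at week 5; 18/12 = 1.50 at week 6)

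**Assumptions, not in the documents:** short-arm loss L of 2, 5 or 8%; the same weekly loss rate in both arms; loss independent of response; nobody rescued by scenario ii; true virological SVR of 90% (standard) and 78% (short), exactly at the margin; two-sided 95% Newcombe interval. The arm sizes, 99 and 93, are the SAP's.

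**Formulas.** Standard-arm loss = 1 - (1 - L)^1.48. Expected ITT SVR = virological SVR × (1 - loss). False non-inferiority is the exact binomial probability that the lower limit exceeds -12%.

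For L = 5%: standard-arm loss is 1 - 0.95^1.48 = 7.3%. ITT SVR is 0.90 × 0.927 = 83.4% and 0.78 × 0.95 = 74.1%, a difference of -9.3 points instead of -12.

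The second case halves the loss rate on treatment. Weighted time is then 0.5 × 0.5 + 12 = 12.25 weeks (short) and 0.5 × 6.5 + 12 = 15.25 weeks (standard), a ratio of 1.245.

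| Short-arm loss | Standard-arm loss, constant rate | Expected ITT difference | False non-inferiority | False non-inferiority, half rate on treatment |
|---|---|---|---|---|
| 0% | 0% | -12.0 | 2.5% | 2.5% |
| 2% | 2.9% | -10.9 | 3.9% | 3.3% |
| 5% | 7.3% | -9.3 | 6.8% | 4.8% |
| 8% | 11.6% | -7.8 | 10.5% | 6.6% |

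Wald intervals give 2.9, 4.3, 7.1 and 10.5% at the constant rate.

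**How much is due to unequal time?** If both arms lost 7.3%, the difference would be -12 × 0.927 = -11.1 points and false non-inferiority 3.7%. So of the 2.7-point shift at L = 5%, 0.9 is dilution that any loss = failure rule causes and 1.8 comes from unequal time.

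**The SAP's counts.** The DSMB section gives 196 randomised: 192 who completed their randomised treatment (99 + 93), plus 4 randomised to 6 weeks and extended to 12. Since 99 + 93 + 4 = 196, nobody randomised is unaccounted for. Taken literally, all 99 standard-arm participants reached week 12. The remaining risk period is then 12 weeks after treatment in each arm, and the ratio is close to 1.

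**The case against.** Much of the case on the other side stands.

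- **Completion.** On a literal reading of the DSMB paragraph the imbalance largely disappears. Completed may be loose wording, because Tables 3 and 15 still plan counts and reasons for stopping treatment; the SAP does not settle it. A reader might infer instead that the 192 were selected for completing treatment. The counts do not support that: all 196 are accounted for, and the four left out are short-arm participants who were extended.
- **Other analyses.** A reader might infer that the plan relies on ITT alone. It does not: mITT and PP non-inferiority are pre-specified, and both drop the lost. But they are secondary, and nothing requires them to agree with ITT. The mITT set is also muddled, because scenarios i and ii are said to cover it although its definition excludes losses.
- **Rescue.** Scenario ii, the 70 to 146 day analysis window for post-treatment week 12, and continued follow-up after stopping drug (Protocol section 4.3) narrow the rule to people who never return. That group still has unequal exposure.
- **Loss rate.** None is given, and everyone randomised has already stayed 5 to 6 weeks. Two-weekly visits and dispensing during the standard arm's extra weeks make lower loss there plausible, which is why the half-rate column is shown.
- **Direction.** The SAP records that the DSMB recommended ending the short arm for inferiority. The possible bias runs the other way, so a false non-inferiority verdict is unlikely here. The reported ITT difference could still understate the short arm's deficit.

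**Conclusion.** The mechanism, the 18.5 v 12.5 weeks and the direction hold, on the condition that weekly loss is similar in the two arms and some participants never return. The effect is small at 2% short-arm loss (about 1 point; false non-inferiority 3.9%, or 3.3% at the half rate). It is material at 5 to 8% (6.8 to 10.5%, or 4.8 to 6.6% at the half rate), against 2.5% with no loss. These figures rest on an assumed loss rate and a true difference exactly at the margin. The flat statement that the primary analysis is biased goes further than the documents allow, because they give no loss rate and can be read as showing no loss during weeks 6 to 12. What remains is a gap in the decision rule: non-inferiority can be claimed without support from any analysis free of the loss = failure rule. This is a cheap improvement.

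**What to change.** 1. Keep loss = failure ITT as the headline estimate. State that non-inferiority is claimed only if the lower limit also exceeds -12% in an analysis that does not score loss as failure. This could be the existing mITT analysis, or an all-randomised analysis in which SVR12 missing through loss is multiply imputed using arm and last HCV RNA status. Keep the imputation model that small: 5% short-arm loss means only about 5 losses there (93 × 0.05) and 7 in the standard arm (99 × 0.073).
2. Correct the Missing Data section so that loss = failure does not apply to the mITT set.
3. Reconcile the statement that 192 completed treatment with the Full Analysis Set, which is defined as all randomised but then fixed at 192, and say whether anyone was lost between weeks 6 and 12.
4. Split the losses by arm, already planned in Tables 3, 5 and 13, into on-treatment and post-treatment.

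The cost is a few sentences in the SAP and at most one added analysis. The downside is a slightly harder non-inferiority claim.

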### **11.2 Assessments of Safety and Efficacy**

The primary analysis will summarise study variables when the last patient recruited has completed 12 weeks follow-up post treatment. This analysis will be reviewed by the Protocol Steering Committee and then presented publicly. Subsequent analyses will be performed up until and at time that the last patient has completed study follow up (or discontinued from the study).

This is a multicentre, randomised study aiming to demonstrate non-inferiority of a 6 week as compared with a 12 week course of sofosbuvir/velpatasvir for recent HCV infection.

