- To evaluate the immunological factors associated with treatment induced clearance and reinfection;
- To evaluate patient interest and attitudes towards long acting parenteral hepatitis C therapy (Long-Acting Hepatitis C Therapy Questionnaire).

Hypothesis

Six weeks treatment with sofosbuvir/velpatasvir is non-inferior to twelve weeks treatment with sofosbuvir/velpastavir as assessed by sustained virological response at 12 weeks post treatment in the intention-to-treat population (SVR12).

Study design (Figure 1)

This is an open label multicentre study. The study consists of a screening phase, treatment phase and follow-up phase to evaluate treatment response and reinfection. Participants will be required to wait a minimum of four weeks from screening before commencing treatment to assess for spontaneous clearance. The maximum wait period allowed between screening and baseline is 12 weeks.

[figure not shown]

Figure 1: Study Schema

Sample size and power

The primary objective of this trial is to establish the non-inferiority of short duration treatment (6 weeks) to the standard duration treatment (12 weeks). Assuming an expected SVR of 90% in the control arm, 113 participants per arm will be required to give 80% chance that the two-sided confidence interval of the difference between regimens has a lower limit greater than -12%.

A total of 250 subjects enrolled and randomised will comprise the intention-to-treat (ITT) population and will form the study population for evaluation of the primary and secondary endpoints.

TYPE OF ANALYSIS

This document describes the primary statistical analysis for REACT study in accordance with protocol version 5.0.

Data Safety and Monitoring Board (DSMB) Analysis

This study has a DSMB to review the progress and safety of the study. The DSMB conducted an interim safety and adherence analysis when the first 50 participants had either reached post-treatment week 12 or dropped out of the study and then when a further 10 per arm reached 12 weeks post treatment. At the second review the DSMB recommended termination of the short arm of the study due to inferiority. At the stage of the DSMB recommendation, a total of 196 participants had been randomised, 192 had completed their randomised treatment, a further 4 were randomised to receive 6 weeks and extended to 12 weeks. Therefore, the primary analysis population will be based on 192 participants (99 in standard Arm, and 93 in shortened arm).

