Primary analysis: Post-treatment week 12

The analysis for the primary endpoint, SVR12, will be conducted after all participants have completed the post-treatment week 12 visit or prematurely discontinued from study. All the safety and efficacy data through to the post-treatment week 12 visit will be cleaned, finalised, and included for the analysis.

GENERAL CONSIDERATIONS FOR DATA ANALYSES

Statistical Methods

Analysis results will be presented using descriptive statistics. For categorical variables, the number (n) and percentage of participants in each category will be presented. For continuous variables, the number of participants (n), mean and standard deviation (SD), median, interquartile range (IQR, Q1-Q3), range (minimum, maximum) will be reported; for inclusion in the manuscript, an appropriate determination will be made depending on the variable, size and distribution of the population studied.

Statistical tests will be 2-sided and performed at the 5% significance level unless specified.

For all efficacy endpoints, means and proportions with two-sided 95% confidence intervals (CI) will be determined. For the analysis of categorical outcomes, Chi-squared tests or exact equivalents (for small numbers) will be used. For comparison of continuous measures, t tests or non-parametric equivalents will be used as appropriate for the observed data distribution. Changes in injecting behaviour between screening, end of treatment and post-treatment week 12 will be compared using the McNemar test (exact binomial probability).

Analysis Sets

Analysis sets define the subjects to be included in an analysis. The number of participants eligible for each analysis set will be provided. Participants who were excluded from each analysis set will be summarised, with reasons for exclusion.

Full Analysis Set (ITT population)

The FAS includes all enrolled participants who were randomised. This will be the analysis set used for the primary efficacy and safety endpoints. Following the DSMB recommendation to cease the study, the primary analysis population will be based on 192 participants (99 in standard Arm, and 93 in shortened arm).

Modified Full Analysis Set

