Use of NEW sterile needle and syringe in last month, n (%)			
All injections			
..Most of the time ^a			
Half of the time			
Some of the time			
Not in the last month			
How many times in last month used a needled/syringe after someone else, n (%)			
None			
One time			
Two times			
3 – 5 times			
More than 5 times			
Who did you share with?, n (%)			
No-one			
Regular sex partner			
Casual sex partner			
Close friends			
Acquaintance			
Other			
How many times in last month has someone used a needled/syringe after you, n (%)			
None			
One time			
Two times			
3 – 5 times			
More than 5 times			
Who were these people that shared after you?, n (%)			
No-one			
Regular sex partner			
Casual sex partner			
Close friends			
Acquaintance			
Other			

^a Denominator – those reporting injecting drug use in last month

STUDY ENDPOINTS

Table 12. Study endpoints and outcomes

Primary endpoint	Non-inferiority of simplified on-treatment monitoring to standard on-treatment monitoring (ITT population)	Included in primary analysis	
Secondary endpoints	Non-inferiority of simplified on-treatment monitoring to standard on-treatment monitoring (mITT population)	Included in primary analysis	
	Non-inferiority of simplified on-treatment monitoring to standard on-treatment monitoring (PP population)	Included in primary analysis	
	Treatment response: ETR, SVR4, SVR24; HCV RNA below the level of quantification through 2 years post treatment	Included in primary analysis	
	Adverse events	Included in primary analysis	
	On-treatment adherence	Included in primary analysis	
	Early treatment discontinuation	Included in primary analysis	
	Relapse and reinfection	Included in primary analysis	
	Resistance associated substitutions (RAS) for people who have failed treatment	Included in primary analysis	
	Laboratory abnormalities	Included in primary analysis	
	Change in HIV RNA and CD4 (on treatment and end of treatment)	Included in primary analysis	
			Included in primary analysis
Additional pre-specified outcomes	Factors associated with on treatment efficacy (only if SVR12 is low)	Included in primary analysis	
	Factors associated with sub-optimal adherence		
	Factors associated with re-infection	Not included in primary analysis	
	To evaluate the impact of treatment on illicit drug use, injecting behaviour and sexual risk-taking behaviour (behavioural survey) during treatment	Not included in primary analysis	

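### SAP Table 12 places SVR24 and the 2-year HCV RNA endpoint in an analysis cut at post-treatment week 12, and Table 2 gives its last HCV RNA window no upper limit

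*SAP*

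**What the plan says.** - **Endpoint list.** One secondary-endpoint row of SAP Table 12 reads "Treatment response: ETR, SVR4, SVR24; HCV RNA below the level of quantification through 2 years post treatment" and is marked as part of the primary analysis. Other rows, such as factors associated with reinfection, are marked "Not included in primary analysis", so the label separates what is analysed now from what is analysed later.
- **Data cut.** Under the SAP heading for the PT week 12 primary analysis, the SVR12 analysis "will be conducted after all participants have completed the post-treatment week 12 visit or prematurely discontinued from study". The next sentence adds: "All the safety and efficacy data through to the post-treatment week 12 visit will be cleaned, finalised, and included for the analysis". Protocol 11.2 has the same timing: "The primary analysis will summarise study variables when the last patient recruited has completed 12 weeks follow-up post treatment".
- **Results shells.** Table 13 has an SVR24 row, with columns for the between-arm difference (95% CI) and a P value. No results table has a row for the 2-year endpoint.
- **Text list.** Under Secondary efficacy endpoints, the SAP lists ETR and then "SVR4 (defined as undetectable plasma HCV RNA at post-treatment week 4". The list stops there.
- **Windows.** Table 2 counts days from the last dose. For HCV RNA, PT week 12 is days 70 to 146. PT week 24 starts at day 147, has an upper limit of NA, and is the last row.
- **Later analyses.** Protocol 11.2 states: "Subsequent analyses will be performed up until and at time that the last patient has completed study follow up".

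**The concern.** Two endpoints are assigned to an analysis that takes place before they can be measured in everyone, and the SAP disagrees with itself on whether they belong there. An analyst following Table 13 would either be unable to fill the SVR24 row or would fill it from whichever participants happened to have reached that visit.

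The open window adds a labelling problem. Any HCV RNA result from day 147 onward, including one taken almost two years after treatment, can be called PT week 24. In a population followed specifically for reinfection, a later reinfection could then be recorded as failure to sustain response at 24 weeks.

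**Working it through.** The plan gives no figure of its own on this point, and the sample-size calculation does not enter into it. The check is visit arithmetic.

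**1. Distance from the cut.** Inputs are from Protocol 4.2. Treatment ends at study week 6 (short) or 12 (standard). PT week = study week minus end-of-treatment week.
- SVR24: 30 − 6 = 24 (short); 36 − 12 = 24 (standard). This is 24 − 12 = 12 weeks past the cut.
- Termination: 102 − 6 = 96 (short); 108 − 12 = 96 (standard). This is 96 − 12 = 84 weeks past the cut.

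**2. Cut by visit.** If data stop at each participant's PT week 12 visit, there are no SVR24 or 2-year results in either arm.

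**3. Cut by calendar date.** Suppose data close when the last participant, taken to be in the standard arm, reaches PT week 12, which is study week 24 for that person. A visit at study week w is not yet due for those who started in the last (w − 24) weeks of accrual.
- SVR24: 30 − 24 = 6 weeks (short); 36 − 24 = 12 weeks (standard).
- Termination: 102 − 24 = 78 weeks (short); 108 − 24 = 84 weeks (standard).

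Share not yet due = those weeks ÷ accrual length A, capped at 100%. The documents give no accrual length, so uniform accrual over three values of A is assumed:

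| A (weeks) | SVR24, short | SVR24, standard | Final visit, short | Final visit, standard |
|---|---|---|---|---|
| 52 | 6/52 = 11.5% | 12/52 = 23.1% | 100% | 100% |
| 104 | 6/104 = 5.8% | 12/104 = 11.5% | 78/104 = 75.0% | 84/104 = 80.8% |
| 156 | 6/156 = 3.8% | 12/156 = 7.7% | 78/156 = 50.0% | 84/156 = 53.8% |

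**4. The PT week 24 window.** Follow-up day = 7 × PT week. PT weeks 24, 36, 48, 60, 72, 84 and 96 are days 168, 252, 336, 420, 504, 588 and 672. All are at or beyond day 147, so all seven scheduled visits fall in PT week 24, and six of them are not the SVR24 visit. No window is labelled for the 2-year endpoint, and no rule says which of several values in a window to use.

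**5. What this can do to one participant.** Take someone suppressed at PT week 12 who misses the week-24 visit and has a quantifiable reinfection at FU1 (day 252). Table 2 labels that result PT week 24. The SAP's missing-data rules fill a gap with suppressed values on both sides, or with a quantifiable value before it. They do not cover a suppressed value followed by a quantifiable one. This participant could therefore be counted as an SVR24 failure.

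**6. Where windows could sit.** Midpoints between adjacent nominal days are 210, 294, 378, 462, 546 and 630. They contain the visit windows in Protocol 6.1 and the Arm A schedule: SVR24 is 168 ± 14 = 154–182, FU1 is 252 ± 28 = 224–280, and Termination is 672 ± 28 = 644–700.

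**The case against.** The case against is substantial. The SAP limits its own scope: "This document describes the primary statistical analysis for REACT study in accordance with protocol version 5.0". Its text list already stops at SVR4, and the Protocol provides for later analyses, so no endpoint is lost. On this view the defect is one over-inclusive table row plus one shell row. If the cut is by visit, the open window collects nothing in this analysis. That is all fair, and it keeps the point to secondary endpoints. It does not reconcile Table 12 and Table 13 with the cut. The SAP also expects later data to be on hand, since a missing SVR12 may be replaced by an SVR24 or later result, so the window cannot be dismissed as idle.

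Four stronger readings are tempting and are not supported:
- **That the results would be biased towards the short arm.** The windows run from last dose in both arms and so do not differ by arm. Unequal follow-up arises only under a calendar cut. A direction would also require not-yet-due visits to be scored as failures, and the SAP's failure rules are written for the primary endpoint only.
- **That a reinfection at PT week 96 would count as an SVR24 failure.** FU1 to FU5 results would normally exist, lie nearer day 168 and, in that scenario, be suppressed. No rule selects the latest value. The FU1 case above is the one that can arise.
- **That a 2-year result would be reported at this cut.** It has a label in Table 12 but no results table. Only SVR24 has a shell.
- **That the primary comparison is compromised.** SVR12 has its own closed window. The only link is the replacement rule for a missing SVR12.

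**Conclusion.** The point holds as an inconsistency in the SAP and an incomplete window table. SVR24 is due 12 weeks, and the final visit 84 weeks, after the data cut of the analysis they are assigned to, and seven scheduled visits share the PT week 24 label. Followed as written, the SVR24 row would be empty, incomplete or mislabelled.

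The percentages not yet due illustrate the calendar-cut reading only. They assume uniform accrual over 52 to 156 weeks with a standard-arm participant last, and they are not matched to the 192 participants in the primary analysis population after the DSMB recommendation. The 6-week difference in post-treatment time under that reading follows from the visit schedule. Its effect on the comparison is not established.

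**What to change.** - **Table 12:** split the row. Keep ETR and SVR4 in the primary analysis. Mark SVR24 and HCV RNA through 2 years "Not included in primary analysis".
- **Table 13:** remove the SVR24 row at this cut. Report SVR24 and the 2-year endpoint at the later analysis foreseen in Protocol 11.2.
- **Table 2:** close the PT week 24 HCV RNA window before FU1, for example at day 209. Add windows for FU1 to Termination, for example 210–293, 294–377, 378–461, 462–545, 546–629 and 630 onward. Other cut-points that respect the Protocol's visit windows would serve equally well.
- **Selection rule:** when several values fall in one window, use the one nearest the nominal day.

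A sentence stating whether the cut is by visit or by calendar date would also settle whether later results are available to replace a missing SVR12.

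The cost is SAP wording and later reporting of two secondary results. No sample size, visit or procedure changes.
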